8.9.3 Analysis of Secondary Endpoints

The analysis of secondary endpoints will be based on the FAS.

The primary efficacy analysis will be repeated for each continuous secondary efficacy endpoint. Further explanatory variables may be included in the modeling depending on the relevance to the endpoint analyzed and will be specified in the SAP.

In addition, for each NGM282 treatment group, the LS mean rate (slope, per week) of change in ALP during Weeks 1–4 will be compared to that during Weeks 5–12; the changes in slopes will be estimated. This estimation will be performed using a MMRM similar to that of the primary efficacy analysis. It will also be repeated using percent change in ALP.

Categorical secondary efficacy endpoints (reflecting incidence and severity of IBD-associated symptoms and acute cholangitis) will be analyzed using confidence intervals of differences of population treatment proportions.

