4 STUDY DESIGN

This is a multiple-center, randomized, double-blind, placebo-controlled, parallel-group study of NGM282 when administered for 12 weeks as a daily subcutaneous (SC) injection in patients with PSC. Approximately 60 subjects will be randomized across approximately 40–45 sites worldwide.

Patients will sign the Informed Consent Form at or prior to the Screening Visit and will undergo screening assessments to verify eligibility for the study (up to 6 weeks). Patients to be studied will have confirmed PSC as defined by an elevated ALP and either liver histology or cholangiography consistent with PSC. The presence of IBD is allowed as well as treatment with a stable regimen of biologic, immunosuppressant, or systemic corticosteroid therapy. UDCA therapy is allowed at stable doses for at least 12 weeks and < 27 mg/kg/day. Patients with decompensated cirrhosis, cholangiocarcinoma (diagnosed or suspected), acute cholangitis, or recently placed bile-duct stents will be excluded from this study. All subjects with concomitant IBD will be required to have had a colonoscopy within 12 months of Screening with no evidence of dysplasia. All subjects will undergo MRCP at Screening.

On Day 1, subjects will be randomized into one of the three treatment arms (NGM282 1 mg, NGM282 3 mg, or placebo) in a 1:1:1 ratio. The randomization will be stratified according to concurrent UDCA or no-UDCA status to ensure an even distribution across the three groups. Study-drug SC self-administration instructions and training will be provided to the subjects and a weekly study-drug kit will be dispensed. Treatment assignment will be blinded to the sites, subjects, Sponsor, and Medical Monitor throughout the study period.

The first dose (Day 1) and doses at Weeks 1, 2, 4, 8, and 12 will be self-administered in the clinic, with all other doses through Week 12 self-administered at home. Self-administration should occur at approximately the same time in the morning for every dose in both the clinic and at home.

Subjects will return to the clinic on Weeks 1, 2, 4, and 8 for on-treatment assessments and to receive weekly study-drug kits. Week 12 will be the End of Treatment (EOT) clinic visit. Subjects will return to the clinic at Week 16 (or 4 weeks after last dose) for an End of Study (EOS) follow-up visit.

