5.2 EXCLUSION CRITERIA

Any of the following will exclude potential subjects from the study:

1. Clinically significant acute or chronic liver disease of an etiology other than PSC.

- a. Patients with stable treated overlapping PSC and autoimmune hepatitis (AIH) will be allowed to enroll into the study.
 - i. Stable treated overlapping PSC/AIH is defined as on a consistent regimen of immunosuppressive therapy for a minimum of 12 weeks and no evidence of a hepatic flare during that time period.
2. Secondary or IgG4-related sclerosing cholangitis
3. Presence of a dominant stricture of **clinical** concern on MRCP at Screening.
 - a. Patients with dominant stricture can be enrolled if the investigator feels there is no evidence on magnetic resonance imaging or cholangiography indicative of cholangiocarcinoma or that the stricture will not result in significant fluctuations in ALP during Screening or Study period.
 - b. Patients with a dominant stricture must have a total bilirubin of ≤ 2.5 mg/dL for at least 6 months prior to Screening.
4. Placement of a bile-duct stent or percutaneous bile-duct drain within 3 months of Screening
 - a. Patients who have undergone a balloon dilation procedure of a stricture will be allowed to enroll into the study after a minimum of 4 weeks post-procedure.
5. History, evidence, or high suspicion of cholangiocarcinoma or other hepatobiliary malignancy based on imaging, screening laboratory values, and/or clinical symptoms
6. Acute cholangitis within 12 weeks of Screening and through Day 1
 - a. Chronic preventive antibiotics for cholangitis will be allowed in the study.
 - b. Intermittent courses of antibiotics for the presumptive treatment of cholangitis are allowed if outside the 12-week window prior to Screening.
7. Evidence of decompensated cirrhosis (Child-Pugh B or C) based on histology, relevant medical complications, or laboratory parameters.
 - a. Patients with compensated cirrhosis will be allowed to enroll into the study.
 - b. Patients with pre-sinusoidal esophageal varices with no history or evidence of bleeding may be enrolled as long as there is no other evidence of hepatic decompensation.
8. Prior liver transplantation
9. Any contraindication or inability to obtain a screening MRCP or colonoscopy (only in patients with concomitant IBD, if historical colonoscopy within the 12-month window is not available)

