8.9.2 Analysis of Primary Efficacy Endpoint

As the primary efficacy analysis, the population mean change in ALP from Baseline to Week 12 will be compared between treatment groups using a mixed-effect model repeated measures (MMRM) analysis of covariance (ANCOVA) of the primary efficacy endpoint, using the FAS. The model will contain treatment group, visit, treatment group by visit interaction, UDCA (yes/no), treatment group by UDCA interaction, and diabetic status as classification variables and the Baseline value as a continuous covariate. An unstructured covariance matrix will be assumed; however, if the modeling using that matrix does not converge, then other matrices will be explored. For each treatment and treatment comparison versus placebo, the least squares mean, associated standard error (SE), 95% confidence interval, and corresponding p-value will be presented. The overall type 1 error rate for the two primary comparisons versus placebo will be controlled using the step-down Dunnett multiple-testing procedure ([Dmitrienko and D'Agostino 2013](#)).

As secondary analyses within the same MMRM, the linear combinations

$$\mu_1 - \mu_3$$

and

$$(\mu_1 + \mu_3)/2 - \mu_p$$

will be estimated, where μ_1 , μ_3 , and μ_p are the population LS means for the primary efficacy endpoint of the 1 mg NGM282, 3 mg NGM282, and placebo groups, respectively.

Further explanatory variables may be included in additional modeling using the FAS, similar to the primary efficacy analysis, depending on the relevance to the endpoint; such modeling will be specified in the SAP.

If strong evidence of marked deviations from normality is noted in the distribution of the residuals of the primary MMRM ANCOVA, then FAS analyses using data transformations of the primary efficacy endpoint, and/or non-parametric approaches, will be explored.

As sensitivity analyses,

- a. The primary analysis for the primary endpoint will be repeated for the PPS.

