7.2. Secondary Efficacy Endpoint

The following endpoints will be analyzed for the FAS.

[figure not shown]
The endpoints among the following that are based on assessments scheduled for more than 1 post-treatment time point, will be analyzed using the FAS. They will be evaluated using MMRM analyses similar to that of the primary endpoint analysis. In contrast, the endpoints among the following based on assessments scheduled at Week 12 only will be evaluated using an ANCOVA model including treatment group, UDCA use, and treatment by UDCA use interaction as classification variables, and the Baseline value as the continuous covariate.

- Percent change from Baseline in ALP at Week 12
- Changes and percent changes from Baseline at Week 12 in the following:
 - ALT, AST, bilirubin (total, direct), and GGT
 - Total cholesterol, HDL cholesterol, LDL cholesterol, and triglycerides
 - Bile-mediated absorption as measured by fat-soluble vitamins

For each NGM282 treatment group, the LS mean rate (slope, per week) of change in ALP during weeks 1-4 will be compared to that during weeks 5-12. Changes in the slopes will be estimated with a MMRM from primary analysis. The same analysis will be done for percent change in ALP.

The relevance of the explanatory variables to each secondary efficacy endpoint will be checked. Similar to the model in the primary efficacy analysis, all relevant explanatory variables will be included into the analysis model with FAS.

The Mayo Partial IBD Score is a non-invasive 9-point partial Mayo score used as an outcome measure for clinical trials assessing therapy for ulcerative colitis. The Mayo Partial IBD Score will be assessed at all study visits. It is administered pre-dose at Day 1 and Weeks 1, 2, 4, 8, 12 and 16 (End of study). Severity of IBD-associate symptoms will be summarized with frequency and percentage.

8. Safety and Tolerability Analysis

Safety and tolerability will be assessed by clinical review and summaries of the following parameters:

1. AEs
2. Clinical laboratory test results
3. Physical examination results
4. LISSAs
5. Electrocardiogram results

6. Pregnancy Test
7. Vital signs

[figure not shown]
All safety and tolerability analyses will be conducted using the Safety Set. Percentage for the safety and tolerability analyses based on the number of subjects with a given event or attribute will be based on the number of subjects who were treated.

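### The early-versus-late ALP slope comparison is planned only within each NGM282 arm, so it describes that arm's profile but cannot show that the drug effect builds or levels off.

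*Protocol*

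**What the plan says.** Protocol section 8.9.3 adds one estimation to the repeat of the primary analysis for the continuous secondary endpoints. It takes, "for each NGM282 treatment group, the LS mean rate (slope, per week) of change in ALP" over Weeks 1–4, which "will be compared to that during Weeks 5–12; the changes in slopes will be estimated". On the model it says: "This estimation will be performed using a MMRM similar to that of the primary efficacy analysis". The same is to be done for percent change in ALP.

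SAP section 7.2 also limits the comparison to the NGM282 groups and says: "Changes in the slopes will be estimated with a MMRM from primary analysis".

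Neither section asks for the slope change in the placebo arm, or for a difference in slope change between a dose and placebo. Neither states a hypothesis, a significance level or an intended interpretation for the slope changes.

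The design supplies what a controlled comparison needs. Under Protocol section 4, "subjects will be randomized into one of the three treatment arms (NGM282 1 mg, NGM282 3 mg, or placebo) in a 1:1:1 ratio". Under section 8.9.2, "The model will contain treatment group, visit, treatment group by visit interaction, UDCA (yes/no), treatment group by UDCA interaction". Chemistry is collected in every arm at Weeks 1, 2, 4, 8 and 12 (Protocol Table 5.5-1).

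**The concern.** A reader who sees a change in slope reported for each dose will naturally take it as an answer to whether that dose's effect on ALP is still growing or has flattened. The specified contrast cannot answer that. If ALP drifts in all arms after enrolment, and drifts differently early and late, the drift passes in full into each active arm's slope change. Having placebo subjects in the model does not help, because an arm's least squares mean at each visit still includes the visit effect common to all arms. Only subtracting the placebo slope change removes it.

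What is at stake is a descriptive statement about the shape of the response, which may inform thinking about treatment duration or later design. The trial's efficacy conclusion at Week 12 does not depend on it.

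**Working it through.** The documents give no power, standard error or effect size for the slope comparison, so there is no stated figure to reproduce. The check has three steps.

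**1. The contrast.** Scheduled ALP values after baseline fall at Weeks 1, 2, 4, 8 and 12. The plan does not say which visits define each slope. Here the early slope is the least squares line through Weeks 1, 2 and 4, and the late slope is the line through Weeks 4, 8 and 12. Late minus early is then a weighted sum of the five visit means, with weights

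c = (0.2857, 0.0714, −0.4821, 0, 0.1250).

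The weights sum to zero, so a constant shift drops out and raw values and changes from baseline give the same answer.

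**2. What the contrast picks up.** Write an active arm's mean profile as the shared profile s plus the drug effect d.

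- Within the active arm: c·(s + d) = c·s + c·d
- Within placebo: c·s
- Difference: c·d

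Example with assumed values: s = (−20, −40, −60, −60, −60) U/L and a constant drug effect of −30 U/L at every visit.

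- c·s = 0.2857(−20) + 0.0714(−40) − 0.4821(−60) + 0.1250(−60) = −5.71 − 2.86 + 28.93 − 7.50 = +12.86 U/L per week
- c·d = −30 × 0 = 0

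The active arm shows a slope change of +12.86 U/L per week and so does placebo. The difference is 0, which is correct because the drug effect does not change over time.

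**3. How often this could mislead.**

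- From Protocol section 8.1: 16 completers per arm and an SD of 200. That SD is stated for the change from baseline within a treatment-by-UDCA cell; using it at every visit is an assumption.
- Also assumed: equal correlation of 0.7 between visits, and a two-sided 5% test. The plan states neither for this analysis.
- Sum of squared weights: 0.0816 + 0.0051 + 0.2325 + 0 + 0.0156 = 0.3348
- Between-subject SD of slope change: 200 × √[(1 − 0.7) × 0.3348] = 63.4 U/L per week
- Within-arm standard error: 63.4/√16 = 15.85
- Standard error of NGM282 minus placebo, equal arms: 15.85 × √2 = 22.4

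If the drug effect is constant and the shared slope change is 0.25 or 0.5 of the between-subject SD, the shared change is 0.25 × 63.4 = 15.9 or 0.5 × 63.4 = 31.7 U/L per week. The noncentrality of a one-sample t test on 15 df is 0.25 × √16 = 1 or 0.5 × √16 = 2, and the rejection probability is 15.5% or 46.5%. The placebo-subtracted contrast rejects 5% of the time in both cases.

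These shared changes are large. If the late slope is flat, placebo ALP would have to fall by 3 × 15.9 ≈ 48 or 3 × 31.7 ≈ 95 U/L between Weeks 1 and 4.

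Smaller changes do less. With SD 200 to 300 and equal correlation 0.5 to 0.9 (same t calculation), the within-arm rejection rate is:

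| Shared slope change (U/L per week) | Within-arm rejection rate |
|---|---|
| 5 | 5–8% |
| 10 | 6–18% |
| 20 | 9–53% |

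Fitting the late slope to Weeks 8 and 12 alone barely alters this: at SD 200 and correlation 0.7 the standard error is 15.95 instead of 15.85. The one-sample test stands in for the MMRM contrast and would not match it exactly.

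**The case against.** The strongest reply is that nothing formal rests on this analysis. It is an added estimation, absent from the listed objectives and endpoints, with no significance level and no claim attached. The null hypothesis and success rule in Protocol section 8.3 concern Week 12 differences from placebo. All of that stands, and it sets the severity. A reader might infer that the trial's efficacy conclusion is compromised; the documents do not support that.

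A second reply is that placebo is visible anyway, because chemistry is summarized by visit and treatment group (Protocol section 8.10.2, SAP section 8.2). A placebo fall that later flattened could be seen there. But those summaries give no slope change and no interval for a difference from placebo, so they do not fill the gap.

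A reader might also take Protocol section 5.2 as evidence that ALP drifts in PSC, since exclusion criterion 3 mentions "significant fluctuations in ALP during Screening or Study period". That text sets a condition for enrolling patients with a dominant stricture, and fluctuation in individuals is not a shared mean trend. It is not evidence of the size or existence of a drift.

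Nor does the entry requirement of Screening ALP above 1.5 times the upper limit of normal establish one. Baseline is the last value on or before Day 1 (SAP section 3), and Day 1 is at least 14 days after Screening (Protocol Table 5.5-1, footnote a). Much of any regression to the mean would therefore precede baseline, though some could remain. The sample-size section assumes zero placebo change at Week 12, but that is a planning assumption and says nothing about slopes.

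Finally, the SAP provided describes the interim analysis and mentions a Full Study SAP that is not among the documents. That plan may add a placebo contrast; Protocol section 8.9.3 does not require one.

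**Conclusion.** The point holds in a limited form. Both documents confine the slope-change comparison to the NGM282 arms, and such a contrast cannot separate a changing drug effect from a time trend shared with placebo. It is sound as a description of each arm and unsound as the basis for saying that the effect builds or levels off.

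That follows from the algebra and needs no assumption. How far it would mislead does: the placebo trend in PSC is not in the documents, and the 16% and 46% rates require an assumed shared change of about 16 or 32 U/L per week. With a shared change of 5 U/L per week the rate stays within 5–8% over the range examined. The documents do not say that the slope change will be read as a drug effect, so the risk is one of interpretation. Severity is low, and the repair is a cheap improvement.

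**What to change.** In Protocol section 8.9.3 and SAP section 7.2 (and in the Full Study SAP, if it does not already do so), estimate the early slope, the late slope and their change in all three arms from the same MMRM. State which visits define each slope. For each dose, report the NGM282-minus-placebo difference in slope change with its 95% CI, for absolute and for percent change in ALP. Keep the within-arm slopes as description, and base any statement about a changing drug effect on the placebo-subtracted contrast.

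The cost is a few sentences and one further set of contrasts from a model already planned, with no new data. The downside is precision: with equal arms the contrast's standard error is √2, about 1.4, times the within-arm one. Under the assumptions above, its 95% CI would be roughly ±1.96 × 22.4 ≈ ±44 U/L per week, so it may well be inconclusive.

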5 SUBJECT SELECTION

5.1 INCLUSION CRITERIA

Patients who meet the following criteria may be included in the study:

1. Males and females between 18 and 75 years of age inclusive who are able to comprehend instructions and follow the study procedures, and are willing to sign an Informed Consent Form (ICF).
2. Confirmed diagnosis of PSC based any **two** of the following three criteria:
 - a. Historical evidence of an elevated ALP > ULN from any laboratory
 - b. Liver biopsy consistent with PSC
 - i. Patients with small-duct PSC on liver biopsy must also have a concurrent diagnosis of IBD
 - c. Abnormal cholangiography consistent with PSC as measured by MRCP, ERCP, or percutaneous transhepatic cholangiography
3. Subjects must have certain additional laboratory parameters in specified ranges at Screening, as follows:
 - a. ALP > 1.5 × ULN
 - b. Total bilirubin ≤ 2.5 mg/dL
 - c. ALT and AST < 5 × ULN
 - d. Serum creatinine < 2 mg/dL or creatinine clearance > 60 mL/min by Cockcroft-Gault calculation
 - e. Platelets ≥ 100 K/uL
 - f. International Normalized Ratio (INR) ≤ 1.3 (in the absence of warfarin or other anticoagulant therapy)
 - g. Carbohydrate antigen 19-9 (CA19-9) ≤ 130 U/mL
 - i. Patients with a CA 19-9 > 130 U/mL may be enrolled if they have two results a minimum of 4 weeks but not greater than 1 year apart and not more than 50 U/mL difference between the two results
4. Patients taking UDCA will be allowed to enroll if meeting the following criteria:
 - a. Total daily dose of < 27 mg/kg/day
 - b. Minimum of 12 weeks of treatment
 - c. No significant dosage changes during 8 weeks prior to Screening
 - d. Minimum of 12-week washout period prior to Screening if UDCA is stopped

5. Patients with concomitant IBD are allowed to enroll upon meeting the following criteria:
 - a. A colonoscopy within 12 months of Screening with no evidence of dysplasia
 - b. No episode of an IBD flare or IBD flare-related bloody diarrhea within 6 months of Screening and through Day 1
 - c. Stable regimen of biologic treatments, immunosuppressive, or systemic corticosteroids (< 10 mg/day) for > 12 weeks prior to Screening and through Day 1
 - i. Vedolizumab is an excluded biologic treatment
6. Female patients are eligible for the study if they meet the following criteria:
 - a. Are not pregnant or nursing

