C4 = 7-alpha-hydroxy-4-cholesten-3-one; CA19-9 = carbohydrate antigen 19-9; ELF = enhanced liver fibrosis; EOS = End of Study; EOT = End of Treatment; ERCP = endoscopic retrograde cholangiopancreatography; HIV = human immunodeficiency virus; IBD = inflammatory bowel disease; INR = International Normalized Ratio; LISSA = local injection-site symptom assessment; MRCP = magnetic resonance cholangiopancreatography; NRS = Numeric Rating Scale; p-ANCA = perinuclear anti-neutrophil cytoplasmic antibodies; PK = pharmacokinetic; Wk = week.

^a There must be a minimum of 14 days between Screening and Day 1 visits for adequate separation of the repeated Chemistry (liver function tests) and INR assessments.

^b Colonoscopy will be performed only in patients with concomitant IBD and who do not have a colonoscopy available within 12 months of Screening.

^c MRCP will be performed in all subjects at Screening.

^d LISSA evaluations will be performed pre-dose for all on-treatment visits.

^e PK blood samples will be collected before subjects dose themselves in the clinic (pre-dose). At Day 1 and Week 12, an additional PK blood sample will be collected 2 hours post-dose.

^f NRS Itch/Fatigue will be completed as a daily diary during Day 1 and Study Weeks 1, 4, and 12. Diary will be dispensed at the study visit prior to the collection week.

^g Mayo Partial IBD Score will be collected in all patients, independent of whether they have IBD or not.

^h A second CA19-9 sample may be collected during the Screening period a minimum of 4 weeks from the original Screening sample in order to meet Inclusion Criteria 3g.

ⁱ A serum pregnancy test will be performed on all female subjects at Screening, Week 12, and Week 16. A urine pregnancy test will be performed on all female subjects at Day 1 (pre-dose).

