5.9.12 Mayo Partial IBD Score

The Mayo Partial IBD Score ([Appendix D](#)) is a non-invasive 9-point partial Mayo score used as an outcome measure for clinical trials assessing therapy for ulcerative colitis ([Lewis et al. 2008](#)). The partial score evaluates changes in stool frequency, rectal bleeding, and physician assessment of disease severity, with defined changes in the score correlating with clinical responses to treatment. The Mayo Partial IBD Score will be assessed by study-site personnel at all study visits in all subjects, including Screening and EOS.

The Mayo Partial IBD Score is to be administered pre-dose at Day 1 and Weeks 1, 2, 4, 8, 12, and 16 (End of Study) as outlined in the Schedule of Study Procedures ([Table 5.5-1](#)).

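### IBD symptom severity is compared with placebo only through undefined proportions; a baseline-adjusted analysis of the 0–9 Mayo Partial score is a cheap addition whose gain depends on how many subjects can score above 0

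*Protocol*

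**What the plan says.** Protocol 3 and 8.9.1 make incidence and severity of IBD-associated intestinal symptoms a secondary objective and endpoint. Protocol 8.9.3 sorts secondary endpoints into two kinds. For the first, "The primary efficacy analysis will be repeated for each continuous secondary efficacy endpoint", which means the baseline-adjusted MMRM. The second kind, which expressly includes IBD symptoms and acute cholangitis, "will be analyzed using confidence intervals of differences of population treatment proportions". The section gives no instrument, cut-point, visit, baseline rule or interval method.

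Protocol 5.9.12 describes the Mayo Partial IBD Score, which "is a non-invasive 9-point partial Mayo score used as an outcome measure for clinical trials assessing therapy for ulcerative colitis". Appendix D shows three items scored 0–3, so the total runs from 0 to 9. It is taken at Screening, Day 1, Weeks 1, 2, 4, 8 and 12, and Week 16. A footnote to Table 5.5-1 adds: "Mayo Partial IBD Score will be collected in all patients, independent of whether they have IBD or not".

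SAP 7.2 discusses this score under secondary efficacy and then plans only this: "Severity of IBD-associate symptoms will be summarized with frequency and percentage". The same section gives MMRM to listed endpoints measured at more than one post-treatment visit, but the Mayo score is not on that list. SAP 1 says the document covers the interim analysis, and SAP 10 refers to a Full Study SAP that is not among the documents.

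**The concern.** An ordered score with a Day 1 value and five on-treatment measurements carries more information than a yes/no split at one visit. With 20 randomized and about 16 completing per arm (Protocol 8.1), intervals for differences of proportions are wide, so a consistent worsening of about a point could go unseen.

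Bowel symptoms are a plausible concern for this drug. In the PBC study described in Protocol 2.4, diarrhea was the most frequent treatment-related event: 21.4% and 25.0% on the two doses against 6.7% on placebo. Stool frequency is one of the three Mayo items.

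The plan does not treat bounded symptom scores alike. SAP 11 records that change-from-baseline MMRM had been planned for the 5-D Pruritus Scale and for pruritus and fatigue before being removed. No reason is given for handling the Mayo score differently.

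**Working it through.** **Plan's own figure.** None exists for this endpoint. The only power statement concerns ALP and is untouched. With the average difference (75 + 475)/2 = 275, SD 200, 16 per arm and alpha 0.027: 275/(200·√(2/16)) = 3.89; 3.89 − 2.21 = 1.68; power 95%, consistent with the stated 90% or more.

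**Inputs from the documents.** 16 completers per arm (Protocol 8.1). IBD prevalence in PSC of 21%–80% (Protocol 2.1.1). Entry rule for subjects with IBD: "No episode of an IBD flare or IBD flare-related bloody diarrhea within 6 months of Screening and through Day 1" (Protocol 5.1), so low scores at Day 1 are likely.

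**Assumptions.** Everything else: effect size, SD, visit-to-visit correlation, share of subjects at 0, and the cut. Alpha is 5% two-sided throughout.

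**Step 1, normal approximation, 0.8 SD shift, 16 per arm.**
- Score, no baseline: 0.8/√(2/16) = 2.263; 2.263 − 1.96 = 0.303; power 62%.
- Score, baseline correlation 0.5: 2.263/√0.75 = 2.613; 2.613 − 1.96 = 0.653; power 74%.
- Proportion scoring at least 1, half of placebo at 0: p = 0.500 against 0.788. Power = Φ[(|Δ| − 1.96·√(2p̄q̄/n)) / √((p₁q₁ + p₂q₂)/n)] = Φ[(0.288 − 0.332)/0.161] = 39%.
- With 20%, 70% or 85% of placebo at 0, the proportion gives 24%, 41% or 36%.

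For 80% power the score needs 25 per arm (19 with baseline), against 40–76 for the proportion. This flatters the score, because it ignores the floor at 0.

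**Step 2, floor included, every subject able to score (simulation, 16 per arm).**
- Rounded score clipped to 0–9, 1-point shift at all five visits, between-subject and visit SD 1: Week 12 cuts 27–38%; baseline-adjusted Week 12 score 50%; mean of five visits 82%. Across the settings tried, the Week 12 score gains 5–15 points over the best Week 12 cut.
- In the same model, the proportion with any on-treatment worsening of at least 2 has 52%, no worse than the Week 12 score.
- Latent-normal score, 0.8 SD shift, 20–70% of placebo at 0: Week 12 proportions 21–44%, Week 12 score 45–70%. At 85% zeros: 23–35% against 33–43%.

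**Step 3, subjects without IBD fixed at 0.** Latent-normal model, 0.8 SD upward shift, correlation 0.5, 16 per arm. Each range covers 30% and 60% of IBD subjects at 0 and, for proportions, four Week 12 cuts.

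| IBD share | IBD subjects per arm | Week 12 proportions | Week 12 score (ANCOVA or rank) | Five-visit mean, sustained effect | Five-visit mean, effect at Week 12 only |
|---|---|---|---|---|---|
| 80% | 0.80 × 16 = 12.8 | 14–34% | 41–47% | 58–74% | 9–10% |
| 50% | 8.0 | 8–19% | 22–26% | 22–41% | 6–7% |
| 21% | 3.4 | 3–7% | 4–6% | 4–10% | 2–3% |

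Against the best Week 12 cut, ANCOVA gains 8–14 points at 80% IBD (41.1 − 33.5; 47.2 − 32.8), 4–9 at 50% (22.5 − 19.0; 25.7 − 17.2) and nothing at 21%.

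**Step 4, direction.** With a downward shift, 80% IBD and 60% of them at 0, ANCOVA at Week 12 equals the best cut (both 26%), while rank-ANCOVA reaches 33%. A rank-based check is therefore worth having.

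**Step 5, timing.** In the 1-point model with non-IBD subjects fixed at 0, the best cut against the five-visit mean is 35–37% against 62% (80% IBD), 20% against 31–33% (50%) and about 7% for both (21%). With every subject able to score, a shift confined to Week 12 gives the five-visit mean 10% against 37% for the best Week 12 cut; a shift at Weeks 8 and 12 gives 24% against 39%.

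**The case against.** Several stronger readings are tempting, and the documents do not support them.

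- A reader might infer that the plan expressly discards ordering, baseline and repeat visits. Protocol 8.9.3 defines no event, so its proportion could be new worsening from Day 1 at any visit, which would use baseline and repeat visits. What is documented is missing definition together with the absence of any model.
- A reader might infer a substantial power loss whoever is analysed. In the settings with the full 1-point shift in every subject, averaging visits gained 25–31 points over the best cut. That needs an effect from Week 1 and a contrast the plan uses for no other endpoint; its MMRM contrast is at Week 12. Steps 3 and 5 show the gain shrinking or reversing.
- A reader might take the score as the only scheduled capture of bowel symptoms. Adverse events are assessed at every visit from Day 1 and graded by CTCAE (Protocol 5.5, 7.1), and SAP 8.1 tabulates gastrointestinal events by Lowest Level Term. Diarrhea would not go unrecorded.
- A reader might conclude from SAP 7.2 that the final analysis has no placebo comparison. That SAP is interim and the full-study plan is not available.

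Protocol 5.9.12 also says that defined changes in the score track clinical response, which favours threshold proportions at least as much as means. Finally, the simulations used two-arm, complete-data ANCOVA, not the plan's full MMRM with unstructured covariance on a floored score. These points limit the size of the concern. They do not supply a definition for the proportions or an analysis that uses the score as collected.

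**Conclusion.** The point holds in a limited form. The only visible placebo comparison for IBD symptom severity is a difference of proportions whose instrument, cut and visit are undefined, and no visible analysis models the one scheduled IBD-specific score. When many subjects can score, a baseline-adjusted Week 12 score gains roughly 5–30 points over Week 12 proportions, depending on the cut and the model. At about 50% IBD the gain over the best cut is only 4–9 points, and at 21% it is nil. All of these figures rest on assumed shifts of 1 point or 0.8 SD with 16 per arm. At a 50% IBD share or below, no method tried reaches usable power. Averaging visits adds more only for a sustained effect and loses power for a late one. Severity is low: the endpoint is an unpowered secondary one.

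**What to change.** In Protocol 8.9.3 and SAP 7.2 (and the full-study SAP):

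- Name the Mayo Partial IBD Score as the instrument for severity. Keep the proportions and the frequency table, and state the event, cut, visit and interval method for the proportions.
- Add a comparison of each NGM282 dose with placebo on the 0–9 score, using the existing repeated-measures model over Weeks 1, 2, 4, 8 and 12 with the Day 1 score as covariate. Report differences with 95% confidence intervals. Make Week 12 the main contrast, as for other endpoints, and the average over Weeks 1–12 supportive.
- Because scores cluster at 0, add a rank-based check stratified by UDCA, such as a van Elteren test.
- Repeat the analysis in subjects with IBD.

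The cost is SAP wording and one further model from an existing template, with its check and subgroup repeat; no new data, visits or subjects are needed. Mean score differences are less readable than percentages, which is why the frequency table should stay, and normal theory is only approximate near the floor, which the rank-based check addresses.
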